1. LIST OF ABBREVIATIONS

Abbreviation	Definition
AE	Adverse Event
AEM	Adverse Event Monitoring
ANOVA	Analysis of Variance
BV	Bivariate
CRF	Chart Review Form
EDP	Exposure During Pregnancy
FDA	Food and Drug Administration
GLM	General Linear Model
HAEM-A-QOL	Hemophilia-Specific Quality of Life Index for Adults
HAEMO-QOL	Hemophilia-Specific Quality of Life Index
ID	Identification
IRB / IEC	Institutional Review Board / Independent Ethics Committee
ISPOR	International Society for Pharmacoeconomics and Outcomes Research
MDE	Minimum Detectable Effect
MV	Multivariate
NIS	Non-interventional Study
OLS	Ordinary Least Squares
PI/Sub-PI	Primary Investigator/ Sub-Primary Investigator
SAP	Statistical Analysis Plan
SAE	Serious Adverse Event

SAS	Statistical Analysis System
SF-36	36 Item Short Form Health Survey
SF-10	10 Item Short Form Health Survey
SOPs	Standard Operating Procedures
SPSS	Statistical Package for the Social Sciences
US	United States

3. ABSTRACT

- **Title:** Understanding Hemophilia A and B Drug Dosage Administration Patterns.
Version 4.0, 16 March 2017
- **Rationale and background:** In recent years newer and extended half-life treatments (e.g. Alprolix, Eloctate, Adynovate) for hemophilia have been approved by the Food and Drug Administration (FDA). These newer, extended half-life treatments require less frequent administrations than standard half-life treatments (e.g. BeneFIX, Xyntha). However, little is known about the real world administration patterns for extended half-life treatments in comparison to standard half-life treatments.
- **Research question and objectives:** To compare the real world administration patterns and resource utilization associated with of standard half-life (e.g. BeneFIX for hemophilia B, Xyntha for hemophilia A) vs extended half-life (e.g. Alprolix for hemophilia B, Eloctate and Adynovate for hemophilia A) agents for the treatment of hemophilia in the U.S.
- **Study design:** This will be a U.S. site-based study in which physician sites are recruited to participate in the study and enroll patients. Participating physicians will conduct a chart review for their enrolled patients and these same patients will respond to a patient questionnaire online via a web survey. In addition, these patients will be consented to supply their insurance claims data to Kantar Health study team for analysis. All survey questionnaires will be in English.
- **Population:** Approximately 30 sites will participate in this study, with 300 patients enrolled (some caregivers expected if eligible patient is under 18 years of age). The approximate distribution of patients by hemophilia type and treatment type is as follows:
- Hemophilia A patients currently receiving Xyntha or another standard half-life treatment for at least six months (n=~75).
- Hemophilia A patients currently receiving Adynovate or Eloctate for at least six months AND have been switched from a standard half-life treatment, and have been on the prior SHL treatment for at least six months (n=~75).
- Hemophilia B patients currently receiving BeneFIX for at least six months (n=~75).
- Hemophilia B patients currently receiving Alprolix for at least six months AND have been switched from BeneFIX, and have been on the prior BeneFIX treatment for at least six months (n=~75).
- **Variables:** Include physician/practice characteristics, patient treatment pattern, patient demographics and patient clinical profile to be collected in the chart review form (CRF); patient demographics, clinical profile, physician-patient relationship, and quality of life reported outcomes to be collected in the patient/caregiver reported questionnaire; and

cost and utilization related to overall health and hemophilia management to be retrieved from claims data provided by patients/caregivers.

- **Data sources:** Study data will come from three sources: (1) the patient/caregiver-reported outcomes and treatment patterns collected in the form of an online survey, (2) the CRF by physicians collected in the form of an online survey, and (3) the data extracted from patient medical and pharmacy claims which will be received as paper files or pdf downloads.
- **Study size:** This study will involve approximately 30 sites and approximately 300 patients. Eligible sites will be activated on an ongoing basis and evaluated continuously as necessary to achieve cohort fulfillment.
- **Data analysis:** Descriptive statistics (means, standard deviations, frequencies, percentages) will be used to characterize the physician and patient sample. Bivariate analyses using one-way Analysis of Variance (ANOVA) or chi-square tests will compare differences in demographics, health characteristics and outcomes (i.e., dosing, disease severity, health-related quality of life, healthcare resource use, costs) between standard half-life vs. extended half-life treatments separately for hemophilia A and hemophilia B patient cohorts. Generalized linear models (with appropriate link function and distribution) will be used to compare outcomes by treatment groups, adjusting for covariates.
- **Milestones:** This study is estimated to take 18 months to complete with final report tentatively expected in late 2018.

4. AMENDMENTS AND UPDATES

The protocol has been amended to incorporate the feedback received from the initial feasibility part of this study. Safety language has been amended to reflect the nature of data capture and participant interaction, and to ensure compliance with the required safety reporting Standard Operating Procedures (SOPs).

5. MILESTONES

Milestone	Planned date
Start of data collection	April 2017
End of data collection	December 2017
Study Close Out	October 2018

6. RATIONALE AND BACKGROUND

Hemophilia A and B are chronic inherited bleedings disorders caused by an X-chromosome linked deficiency in coagulation factors.¹ Although the incidence of hemophilia is relatively low, it imposes a high level of burden to sufferers, caregivers, and society. As hemophilia requires lifetime treatment it is associated with substantial costs, particularly direct costs. Factor replacement therapy, used for both prophylaxis and on-demand therapy, is the mainstay of hemophilia treatment and has been estimated to cost more than \$250,000 per adult in the United States. Depending on the disease severity and treatment regimen, factor replacement products accounts for 45% to 93% of the total medical costs for hemophilia.²

Newer, extended half-life treatments for hemophilia have recently been approved by the FDA). Alprolix is an extended half-life treatment that was approved by the FDA in March, 2014 for hemophilia B. And similarly, for hemophilia A, Eloctate was approved in 2014 and Adynovate in 2015. These newer, extended half-life drugs require less frequent administrations than Pfizer's BeneFIX (for hemophilia B) and Xyntha (for hemophilia A). Even a relatively small change in frequency of administration has the potential to translate into 50 or fewer infusions per year and a correspondingly smaller number of units infused per patient. The expected advantages of fewer infusions from extended half-life products include greater patient compliance, less disruptions in daily activities and less reliance on others to help with infusions.¹ However; these benefits are only realized if there is indeed fewer infusions associated with the extended half-life products compared with the standard half-life products. To date, little is known about real world administration patterns for extended half-life treatments in comparison to standard half-life treatments. Pfizer is seeking to understand whether Alprolix, Eloctate, and Adynovate are being dosed more often than their labeling indicates, thus potentially costing payors and patients more money compared to traditional treatments, like BeneFIX and Xyntha.

7. RESEARCH QUESTION AND OBJECTIVES

The study's primary objective is to compare the dosing and resource utilization patterns of standard half-life treatments vs. extended half-life treatments for the management of hemophilia A and B

- Specifically, the dosing and resource utilization patterns of Xyntha (or other standard half-life treatments) vs. Adynovate or Eloctate will be assessed for treatment of hemophilia A
- And similarly, the dosing and resource utilization patterns of BeneFIX (standard half-life) vs. Alprolix (extended half-life) will be assessed for treatment of hemophilia B

8. RESEARCH METHODS

8.1. Study design

This study will be conducted as a prospective observational, cross-sectional epidemiological study in U.S. site-based clinical practice settings. Participating physicians / clinicians at approximately 30 sites will enroll approximately 300 patients for inclusion in the study. Participating patients – or their caregiver in the case of patients under the age of 18 - will be consented to participate. After this consent occurs, the physicians will complete a retrospective chart review on each enrolled patient, entering their findings into a chart review form (CRF) online. Patients will complete a one-time study questionnaire, which should take approximately 20 minutes to complete, by accessing a link online. The patient questionnaire will include self-report questions regarding patient demographics, clinical profile, treatment, and physician-patient relationship, along with several validated scales to assess health-related quality of life. In addition, patients will submit their health insurance claims data to the study team for analysis. All survey questionnaires will be in English. All respondents will be provided remuneration for their participation.

8.2. Setting

The study will occur in a site-based clinical practice setting, meaning that patients will be recruited by physicians to participate in the study. Eligible sites will be activated on an ongoing basis and evaluated continuously as necessary to achieve cohort fulfillment. Sites will identify patients according to criteria specified within protocol and patients will further be qualified within the web questionnaire. The Kantar Health research team will closely monitor patient enrollment between sites to ensure equal distribution across the four cohorts is achieved. If needed, additional sites will be contracted and activated to meet total cohort sample size. All physician and patient materials will be completed online via a web-link to a survey provided by Kantar Health.

8.2.1. Inclusion criteria

Physician/Clinician Participants

Participating sites must undergo a contracting procedure and agree to follow the study protocol as well as all terms of the study contract. Participating sites will be led by a physician / clinician (e.g. nurse, nurse practitioner, physician assistant, etc.) who will serve as that site's PI/sub-PI. The participating PI/sub-PI must meet all the following inclusion criteria to participate in the study:

- Must be a healthcare provider with at least 60% of time spent in direct patient care;
- Board-certified or eligible with a Specialty in Hematology or Hematology-Oncology (if hematologist-oncologist, at least 10% practice is dedicated to treatment of hemophilia);
- Currently manages at least 10 hemophilia A and/or B patients;
- Must not be on the FDA debarment list.

Patient Participants

Participants must meet all of the following inclusion criteria to be eligible for inclusion in the study:

- Willing and able to provide informed consent.
- Diagnosed with hemophilia A or B.
- Current disease severity is either moderately severe or severe with a clotting factor level of $\leq 5\%$.
- If suffering from hemophilia A, must be currently taking Xyntha (or another standard half-life treatment), Adynovate or Eloctate for at least six months.
 - If currently taking Adynovate or Eloctate, must have been switched from a standard half-life treatment and had been on that prior treatment for at least six months.
- If suffering from hemophilia B, must be currently taking BeneFIX or Alprolix for at least six months.
 - If currently taking Alprolix, must have switched from BeneFIX and had been on that prior treatment for at least six months.
- Infuse at least 3 times per month

1. In the event of a caregiver responding on behalf of the patient, the above inclusion criteria will be applied for the patient for whom the caregiver is responding.

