8.3. Variables

Below is the current list of variables to be assessed in the in the study:

Physician Participants

Physician/Practice Characteristics

- Primary medical specialty;
- Board certification;
- Percentage of time spent in direct patient care;
- Percentage of their practice dedicated to the treatment of hemophilia;
- Number of moderate to severe hemophilia A and B patients currently managed;
- Number of hemophilia A and B patients currently participating in clinical trials;
- Insurance plans accepted.

Patient Treatment Pattern

- Current and previous hemophilia treatment;
- Reasons for discontinuation;
- Duration of treatment used;
- Whether prescription was prophylaxis or on-demand;
- Number of infusions per month prescribed;
- Frequency of doctor visits for management of hemophilia.

Patient Clinical Profile

- Height and Weight;
- Age of diagnosis;
- Primary symptoms;
- Disease severity;
- Joint health score;
- Comorbidities.

Patient Participants:

Patient Demographics

- Sex;
- Age;
- Race/ethnicity;
- Marital status;
- Household income;
- Education;*
- Employment status;*
- Health insurance type;
- Healthcare insurer;
- Pharmacy insurer.

*In the case of caregivers responding, caregiver's education and employment will also be collected.

Patient Clinical Profile

- Disease severity;
- Clotting factor level.

Patient Treatment

- When are infusions done;
- Number of infusions in a typical month;
- Previous and current hemophilia treatments;
- Duration of previous and current hemophilia treatments used;
- Recent Factor Use Behavior;
- Whether participated in clinical trials within the past 12 months.

Physician Patient Relationship

- Patient's relationship with his/her physician in regards treatment decisions for hemophilia rated as either paternalistic, informative, interpretive, or deliberate depending upon which relationship description the patient selects.

Validated Scales for Health-Related Quality of Life

- 36 Item Short Form Health Survey (SF-36 (adult)).³
- 10 Item Short Health Survey (SF-10 (caregiver reported for child)).⁴
- Hemophilia-Specific Quality of Life Index for Adults (HAEM-A-QOL (adult)).⁵
- Hemophilia-Specific Quality of Life Index (HAEMO-QOL (caregiver reported for child)).⁶

Health Insurance Claims Data from Patients

- Total services and healthcare costs (healthcare visits, factor).
- Hemophilia-specific services and costs (healthcare visits, factor).

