8.5. Study size

The study will involve approximately 300 patients recruited from approximately 30 participating sites.

This study will compare Xyntha vs. Eloctate /Adynovate among hemophilia A patients and Alprolix vs. BeneFIX among hemophilia B patients. For a mean difference comparing two independent means with the anticipated sample sizes (75 vs. 75; 150 total) with $\alpha=0.05$, two-sided, 80% power, the expected minimal detectable effect (MDE) would be Cohen's $d=0.46$. This study with the anticipated sample size is powered to detect at least a moderate effect size.

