When diagnosed with hemophilia	Infancy 0-12 months							
	Toddler 1-3 years							
	Preschool 3-5 years							

Protocol # B1821056  
 Statistical Analysis Plan

**Table 3. Example bivariate table: Patient health characteristics, disease characteristics, and treatment history among hemophilia A patients by standard half-life vs. extended half-life treatment (from patient chart). Note: a similar table would be created for hemophilia B patients.**

	Treatment Group							
	Standard Half-Life		Extended Half-Life		Total			
	% / Mean	N/ SD	% / Mean	N/ SD	% / Mean	N/ SD		
Grade school 5-12 years Teen 12-18 years Young adult 18-21 years <21 years Don't know								
Comorbidities	Joint disease High blood pressure High cholesterol Heart disease Diabetes HIV Hepatitis Other (specify) None of above							
Currently taking medication for joint disease?	Yes No							
Current disease severity	Moderate hemophilia (1-5% factor level) Severe hemophilia (Less than 1% factor level)							
Current primary symptoms	Excessive bleeding after cuts, injuries, or medical procedures Unexplained nosebleeds Excessive bruising Joint pain, swelling, or tightness Blood in stool or urine Other None of the above							
Current joint	Score							

Protocol # B1821056  
 Statistical Analysis Plan

**Table 3. Example bivariate table: Patient health characteristics, disease characteristics, and treatment history among hemophilia A patients by standard half-life vs. extended half-life treatment (from patient chart). Note: a similar table would be created for hemophilia B patients.**

		Treatment Group							
		Standard Half-Life		Extended Half-Life		Total			
		% / Mean	N/ SD	% / Mean	N/ SD	% / Mean	N/ SD		
health score	Don't know								
Joint health score system	Hemophilia Joint Health Score (HJHS)  World Federation of Hemophilia (WFH) score  Other joint scoring system (specify)								
Current factor	Advate  Adynovate  Afstyla  Eloctate  Helixate FS  Hemofil M  Kogenate FS  Kovaltry  Monoclate-P  Novoeight  Nuwiq  Recombinate  Xyntha solofuse  Other, specify								
How factor prescribed	Prophylactically  On-demand  Both prophylactically and on-demand								
Duration of current factor prescribed									
Number of infusions per month									
Prior treatment	Advate  Adynovate  Afstyla  Eloctate  Helixate FS  Hemofil M								

Protocol # B1821056  
 Statistical Analysis Plan

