**Table 3. Example bivariate table: Patient health characteristics, disease characteristics, and treatment history among hemophilia A patients by standard half-life vs. extended half-life treatment (from patient chart). Note: a similar table would be created for hemophilia B patients.**

	Treatment Group						p-value	
	Standard Half-Life		Extended Half-Life		Total			
	% / Mean	N/ SD	% / Mean	N/ SD	% / Mean	N/ SD		
Kogenate FS								
Kovaltry								
Monoclate-P								
Novoeight								
Nuwiq								
Recombinate								
Other, specify								
Was not taking another treatment previously								
Duration of former factor prescribed								
Reasons for discontinuation	Cost/insurance coverage issues							
	[IF PATIENT IS UNDER 18] Patient developed inhibitors to treatment							
	Doctor recommendation							
	Patient preferred a different infusion frequency							
	Other							
	Don't know							
Frequency of visits (non-infusion)	Several times a month							
	Once a month							
	Every three months							
	Every six months							
	Once a year							
	Less than once a year							

Protocol # B1821056  
 Statistical Analysis Plan

**Table 4. Example bivariate table. Patient health characteristics, disease characteristics, and treatment history among hemophilia A patients by standard half-life vs. extended half-life treatment (patient-reported). Note: a similar table would be created for hemophilia B patients.**

		Treatment Group							
		Standard Half-Life		Extended Half-Life		Total			
		% / Mean	N/ SD	% / Mean	N/ SD	% / Mean	N/ SD		
Severity	Mild hemophilia Moderate hemophilia Moderately severe hemophilia Severe hemophilia								
Clotting factor level	6% to 40% 1% to 5% Less than 1%								
Current treatment	Advate Adynovate Afstyla Eloctate Helixate FS Hemofil M Kogenate FS Kovaltry Monoclate-P Novoeight Nuwiq Recombinate Xyntha solofuse Other, specify								
Duration of current factor prescribed									
When infuse	On regular basis to prevent bleeding episodes Whenever or as needed when there is a bleeding episode Both, on a regular basis to prevent bleeding episodes as well as whenever as needed when there is a bleeding episode								
Prior treatment	Advate Adynovate								

Protocol # B1821056  
 Statistical Analysis Plan

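### The severity entry rule uses a grade the SAP's chart categories lack and its patient-reported categories set apart from moderate, so eligibility at a 1-5% factor level is not determined

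*Protocol*

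**What the plan says.** The patient criteria in Protocol 8.2.1 open with "Participants must meet all of the following inclusion criteria to be eligible for inclusion in the study", so every item must be satisfied. One item reads "Current disease severity is either moderately severe or severe with a clotting factor level of" 5% or less. SAP 2.2 carries the same item.

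The SAP shows severity from two sources, both in example tables under 6.2.2:

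- Table 3, from the patient chart, has two grades, each tied to a factor level: "Moderate hemophilia (1-5% factor level) Severe hemophilia (Less than 1% factor level").
- Table 4, patient-reported, has four grades with no factor level attached: "Mild hemophilia Moderate hemophilia Moderately severe hemophilia Severe hemophilia". Clotting factor level is a separate row, with the bands "6% to 40% 1% to 5% Less than 1"%.

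On screening, Protocol 8.2 says that sites identify patients by the protocol criteria and that "patients will further be qualified within the web questionnaire". Neither document defines *moderately severe*, maps it to the chart grades, or says whether the chart or the questionnaire decides. Protocol Appendix 1 lists the patient questionnaire and the physician CRF as still in design.

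**The concern.** The rule joins a label to a number, and at 1-5% the two need not agree. Table 3 uses the same row name as the criterion (current disease severity), so a site will naturally look to the chart grade. There a patient at 1-5% is *moderate*, which is not a permitted label. The only list that contains the permitted label is the patient's own rating, where *moderate* is a different answer from *moderately severe*.

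About 30 sites could resolve this in different ways, so the enrolled population would not be well defined. In a non-randomised comparison of standard and extended half-life products, it matters which patients enter each group. The self-rating is also collected after at least six months on the product being compared, so it is a less secure basis for entry than a charted factor level.

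**Working it through.** **The plan's only design figure.** Protocol 8.5 gives a minimal detectable effect of d = 0.46 for "anticipated sample sizes (75 vs. 75; 150 total"), two-sided alpha 0.05 and 80% power. By the normal approximation, d = (1.960 + 0.842) × √(2/75) = 0.457; by the two-sample t-test, d = 0.460. The figure reproduces. It does not bear on this point: cohorts are filled to about 75 each however the rule is read, so the issue is who is enrolled, not how many.

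**Applying the rule.** The inputs are the entry rule (Protocol 8.2.1), the chart grades (SAP Table 3) and the self-rated grades (SAP Table 4). Three readings are tried:

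1. Factor level alone: 5% or less passes.
2. Chart label, literally: the Table 3 grade must be *moderately severe* or *severe*.
3. Self-rating, literally: the Table 4 grade must be *moderately severe* or *severe*, with a level of 5% or less.

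| Factor level | Self-rated grade | Chart grade | 1. Factor level | 2. Chart label | 3. Self-rating |
|---|---|---|---|---|---|
| 1-5% | Mild | Moderate | pass | fail | fail |
| 1-5% | Moderate | Moderate | pass | fail | fail |
| 1-5% | Moderately severe | Moderate | pass | fail | pass |
| 1-5% | Severe | Moderate | pass | fail | pass |
| <1% | Mild | Severe | pass | pass | fail |
| <1% | Moderate | Severe | pass | pass | fail |
| <1% | Moderately severe | Severe | pass | pass | pass |
| <1% | Severe | Severe | pass | pass | pass |

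A level of 6-40% fails under readings 1 and 3 and has no category in Table 3.

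Of the 4 combinations at 1-5%, reading 1 passes 4, reading 2 passes 0 and reading 3 passes 2. Of all 8 combinations, the three readings agree in only 2, both below 1%. These are counts of combinations, not of patients: the documents give no distribution of self-rated severity within a factor level, so they cannot be turned into a proportion of the sample.

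**Which reading is intended.** A bound of 5% would do no work if only levels below 1% could enter, and Table 3 sets aside a row for 1-5%. Both point to the 1-5% group being eligible. The physician variable in Protocol 8.3, "Number of moderate to severe hemophilia A and B patients currently managed", fits this but is weak support, because it describes a caseload rather than an entry rule.

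**The case against.** The best reply is that this is a slip of terminology. The criterion can be read as severity defined by the stated factor level, applied first by the sites, and Table 3 fits that reading. The 1-5% row would always be empty if the chart label were applied literally. The *mild*, *moderate* and 6-40% rows of Table 4 hint that the self-rating may not screen anyone, although they may simply list the response options. SAP 6.2.2 compares severity between treatment groups, so an imbalance in charted severity would be visible, and 6.2.3 could adjust for it.

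Much of this stands, and it rules out three stronger readings that a reader might infer:

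- *Patients are screened out on self-rated severity.* Protocol 8.2 names no questionnaire item as a screener, the instruments are not available, and the categories come from example tables.
- *The whole 1-5% group is lost.* This follows only from the literal chart label, which the SAP's own table contradicts.
- *Entry depends on the product's effect and so biases the comparison.* No passage says what the Table 4 severity item measures or that it varies by product. Any figure for imbalance between the groups would come entirely from assumed response rates.

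What the reply does not remove is that the reading it relies on is not written down. Nor do the analyses guarantee a remedy: SAP 6.2.3 adjusts only for variables found relevant in the bivariate analyses, so severity is not assured a place in the models, and adjustment cannot bring back patients who were never enrolled.

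**Conclusion.** The point holds as an inconsistency between the entry rule and the SAP's own severity categories. Taken literally, the rule gives conflicting eligibility for patients with the same qualifying factor level: at 1-5%, none, some or all pass depending on the source used. The evident intent is that they are eligible. The effect on the comparison has no computable size, and neither its existence nor its direction is established. The conclusion assumes that the SAP's example tables reflect the categories the instruments will use. It should be corrected before enrolment because the remedy is cheap and makes selection uniform across sites, not because bias has been demonstrated.

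**What to change.** Reconcile Protocol 8.2.1 and SAP 2.2 with SAP Tables 3 and 4:

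- Make the charted factor level the deciding item: 5% or less, recorded as 1-5% or below 1%.
- Drop *moderately severe*, or state which chart grade it corresponds to.
- State in Protocol 8.2 that self-rated severity in the web questionnaire does not override the charted level.
- In SAP 6.2.3, include charted severity (1-5% versus below 1%) as a covariate in the multivariable models whatever the bivariate result, and report the self-rating descriptively.

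One detail needs care. Protocol 8.3 lists clotting factor level only among the patient-reported items; on the chart side it appears through the Table 3 severity bands. The text should therefore name that banded chart grade as the record of factor level.

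The cost is about one line in each document, plus the covariate statement in the SAP. No new data are needed if the CRF follows Table 3, and the instruments were still in design. The population will be slightly broader than a literal reading of the label would give.

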### Physician/Clinician Participants Inclusion Criteria

Participating sites must undergo a contracting procedure and agree to follow the study protocol as well as all terms of the study contract. Participating sites will be led by a physician / clinician (eg, nurse, nurse practitioner, physician assistant, etc.) who will serve as that site's PI/sub-PI. The participating PI/sub-PI must meet all the following inclusion criteria to participate in the study:

- Must be a healthcare provider with at least 60% of time spent in direct patient care
- Board-certified or eligible with a Specialty in Hematology or Hematology-Oncology (if hematologist-oncologist, at least 10% practice is dedicated to treatment of hemophilia)
- Currently manages at least 10 hemophilia A and/or B patients
- Must not be on the FDA debarment list

Protocol # B1821056  
Statistical Analysis Plan

Patient Participants Inclusion Criteria

Participants must meet all of the following inclusion criteria to be eligible for inclusion in the study:

- Willing and able to provide informed consent
- Diagnosed with hemophilia A or B
- Current disease severity is either moderately severe or severe with a clotting factor level of  $\leq 5\%$
- If suffering from hemophilia A, must be currently taking Xyntha (or another standard half-life treatment), Adynovate or Eloctate for at least six months.
  - If currently taking Adynovate or Eloctate, must have been switched from a standard half-life treatment and had been on that prior treatment for at least six months.
- If suffering from hemophilia B, must be currently taking BeneFIX or Alprolix for at least six months.
  - If currently taking Alprolix, must have switched from BeneFIX and had been on that prior treatment for at least six months.
- Infuse at least 3 times per month

In the event of a caregiver responding on behalf of the patient, the above inclusion criteria will be applied for the patient for whom the caregiver is responding.

Patient Participants Exclusion Criteria

Currently enrolled in a clinical trial and/or using investigational product for the treatment of his or her hemophilia

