#### **3.2. Subgroups**

Subgroups will include the different treatment cohorts as defined above under “Treatment/cohort levels” and outlined again below.

- Patients on Xyntha (or other standard half-life treatments) vs. Adynovate or Eloctate (extended half-life treatments) for treatment of hemophilia A
- Patients on BeneFIX (standard half-life treatment) vs. Alprolix (extended half-life treatment) for treatment of hemophilia B

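### Prior-treatment rules bind only the extended half-life cohorts, so returners and recently started patients are pooled into the standard half-life cohort, which may bias the infusion and cost comparison

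*Protocol*

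**What the plan says.** Two rules have to be kept apart.

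- **Current product, all cohorts.** In hemophilia A a patient "must be currently taking Xyntha (or another standard half-life treatment), Adynovate or Eloctate for at least six months" (Protocol 8.2.1). SAP 2.2 has the same for hemophilia B: "If suffering from hemophilia B, must be currently taking BeneFIX or Alprolix for at least six months".
- **Prior product, EHL cohorts only.** A hemophilia A patient on Adynovate or Eloctate "must have been switched from a standard half-life treatment and had been on that prior treatment for at least six months". An Alprolix patient must have come from BeneFIX after at least six months on it.

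For SHL patients the Protocol abstract gives only the current-product condition, for example "Hemophilia B patients currently receiving BeneFIX for at least six months". The sole patient exclusion (Protocol 8.2.2) concerns current trial participation or investigational product.

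SAP 3.2 groups by current product: "Patients on BeneFIX (standard half-life treatment) vs. Alprolix (extended half-life treatment) for treatment of hemophilia B". SAP 6.2.2 and 6.2.3 do the same and plan no stratum, flag or sensitivity analysis by earlier treatment. Prior product, treatment durations and reasons for discontinuation are collected (Protocol 8.3, SAP 4.1) and shown by group in SAP Tables 3 and 4. The limitations in Protocol 8.9 cover recall and self-presentation only.

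**The concern.** The two sides of each comparison are selected differently. Everyone in an EHL cohort has switched and has stayed on the new product for at least six months. Someone who tried EHL and went back is missing from that cohort and, six months later, can be counted in its comparator. The SHL cohort can also hold patients only six months into their first product, whereas every EHL patient has at least 12 months of factor treatment.

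The main outcomes are infusion frequency, resource use and cost. The discontinuation reasons listed in SAP Table 3 include insurance or cost problems and a preference for a different infusion frequency, so leaving a product may be related to the outcomes being compared. Part of any SHL–EHL difference could then reflect who stayed on EHL rather than how the products are used.

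**Working it through.** **1. Applying the criteria.** Assume that severity, infusion frequency and the other criteria are met.

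- BeneFIX, then Alprolix, then BeneFIX again for six months: eligible, analysed as SHL.
- Six months into a first SHL product: eligible, analysed as SHL, with 6 months of total treatment. The EHL minimum is 6 + 6 = 12 months.
- Many years on a single SHL product: eligible, an ordinary SHL user. This patient also falls in the row "Was not taking another treatment previously" of SAP Tables 3 and 4, so that row alone does not identify the recently treated.
- Alprolix as a first product: in neither cohort.

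**2. Is there time for returners?** Alprolix was approved in March 2014, and data collection starts in April 2017. A returner enrolled at the start must have left EHL by October 2016, 31 months after that approval. The window is limited but open.

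**3. Can adjustment deal with it?** SAP 6.2.3 takes covariates from the bivariate results and does not name prior treatment. In hemophilia B every Alprolix patient has BeneFIX as prior product by eligibility, so prior product is nearly aliased with treatment. In hemophilia A an SHL patient may have come from another SHL product, so there is some overlap.

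**4. The plan's own figure.** Protocol 8.5 takes "75 vs. 75; 150 total" "with $\alpha=0.05$, two-sided, 80% power" and gives d = 0.46. Check: (1.960 + 0.842) × √(1/75 + 1/75) = 0.457; the noncentral t gives 0.460. The figure reproduces, and the sample-size statement is not at fault.

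**5. Size of a possible shift.** Let f be the share of SHL patients who are returners or recently started, and δ their mean difference from other SHL users in SD units. Neither is in the documents. The unadjusted shift is f × δ. For the assumed ranges f = 5–40% and δ = 0.25–1.0, of either sign:

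| f | δ | Shift (SD) | Share of 0.46 | Type I error if no true difference | Power at 0.46 if the shift is toward the null |
|---|---|---|---|---|---|
| 5% | 0.25 | 0.013 | 3% | 5.1% | 77.7% |
| 10% | 0.5 | 0.05 | 11% | 6.1% | 70.3% |
| 20% | 0.5 | 0.10 | 22% | 9.3% | 59.1% |
| 40% | 1.0 | 0.40 | 87% | 68.2% | 6.5% |

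**6. The same in infusions, again on assumptions.**

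- SHL side: if 5–15% of 75 (about 4 to 11 patients) are returners infusing 2–4 more times a month than other SHL users, the SHL mean rises by 0.05 × 2 = 0.1 to 0.15 × 4 = 0.6 per month.
- EHL side: let a share q = 0.15–0.35 of switchers infuse 12 rather than 8 times a month, and a share r = 0.3–0.6 of those return to SHL. The mean among those who stay is [8(1−q) + 12q(1−r)]/(1−qr), against 8(1−q) + 12q for all switchers. At q = 0.15, r = 0.3: 8.06/0.955 = 8.44 against 8.60, a gap of 0.16. At q = 0.35, r = 0.6: 6.88/0.79 = 8.71 against 9.40, a gap of 0.69.

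The signs here follow from assuming that leavers infuse more. No cost shift can be calculated.

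**7. Precision if such patients are left out** (noncentral t, 75 EHL patients): 5% dropped leaves 71 SHL patients, detectable effect 0.467, power at 0.46 of 78.8%; 10% leaves 68, 0.472, 77.9%; 20% leaves 60, 0.489, 75.1%.

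**The case against.** The strongest defence is that the study describes current real-world use in a cross-sectional design. A patient back on BeneFIX for six months is a BeneFIX user, and counting him there is not misclassification. That stands, and it is why the all-SHL comparison should remain. It does not make the two cohorts alike in how they were selected, and the background sections go on to interpret the comparison as bearing on the benefit and cost of EHL products.

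It can also be said that the necessary data are collected and tabulated. True, but no planned analysis uses them for this purpose, and without a prespecified rule these patients would be handled after results are seen.

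Several stronger readings are tempting and are not supported:

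- **That staying on the product is required of EHL patients only.** Six months on the current product binds all four cohorts.
- **That the selection must favour EHL.** The listed reasons for stopping include insurance or cost issues and a doctor's recommendation, neither of which implies heavier infusion. The direction in step 6 is assumed.
- **That the SAP expects returners because Adynovate and Eloctate appear among prior products.** The tables are examples and look like answer menus: Table 4 also lists mild disease and a 6–40% factor level, which eligibility rules out. Entry of returners follows from the criteria, not from these lists.
- **That everyone without a prior product is a problem.** Long-term single-product users are ordinary SHL patients.
- **That adjustment can never help.** The aliasing argument is strong in hemophilia B only.

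**Conclusion.** The concern holds as a selection risk. The prior-product rule is one-sided, and as written each comparison sets patients who switched to EHL and stayed against a mixed SHL group that can include EHL returners and patients with under 12 months of treatment. Planned covariate adjustment is not a dependable remedy.

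Whether this biases the results, by how much and in which direction cannot be determined from the documents. Over the assumed ranges the shift runs from negligible (0.013 SD) to serious (0.40 SD); middle values give 0.05–0.10 SD, or 11–22% of the detectable effect. All of these rest on assumed shares and differences. The point deserves action because the remedy needs no new data, not because a bias has been demonstrated.

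**What to change.** 1. **SAP 3.2 and 6.2.3.** Keep the all-SHL comparison. Prespecify, within each hemophilia type, a sensitivity analysis of infusions and costs that excludes SHL patients whose prior product was EHL and those with less than 12 months of total (current plus prior) factor treatment. Keep long-term single-product SHL users. State the detectable effect for the reduced number: about 0.47–0.49 if 5–20% are dropped, an assumed share.
2. **SAP tables.** Report EHL-to-SHL returners as their own row, with infusions per month and reason for discontinuation.
3. **Conclusion and Protocol 8.9.** Word the comparison as current SHL users versus patients who switched to EHL and stayed at least six months, and list this selection as a limitation. Restricting the SHL side does nothing about EHL leavers being absent from the EHL cohort, so only the wording covers that half.

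The cost is SAP wording, one more table row and slightly lower precision in the sensitivity analysis (power at d = 0.46 of about 75–79% for the same assumed shares).
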